2.1 Primary Objective

The primary objective of LABS-2 is to use standardized techniques and measures to assess the longer-term safety and efficacy of bariatric surgery by:

1. comparing post-surgical outcomes to pre-operative status
2. examining risks and benefits of surgery.

LABS-2 will determine the associations between clinical/demographic patient characteristics, components of the surgical procedure, and peri-operative and post-operative care with post-operative risks and changes in patient status.

The principal domains of research interest are delineated below and relate to achieving weight loss and changes in clinical and metabolic co-morbidities of obesity, psychosocial parameters, and quality of life. Additionally, post-operative sequelae as a result of undergoing surgery will be examined. These outcomes will be assessed prospectively for up to 7 years across a multi-center cohort of participants.

Weight Loss and Body Composition. The primary intent of bariatric surgery is to induce weight loss. The ability of bariatric surgery to meet this goal will be assessed by maximum weight loss and long-term patterns of weight loss or regain. LABS-2 will examine differences in weight loss, fat mass and fat-free mass, and waist and neck circumferences based on gender (hypothesizing greater weight loss in men (Ballantyne 2003)), diabetes mellitus (hypothesizing less weight loss among patients with diabetes (Perugini 2003, Schauer 2003)), pre-operative and post-operative physical activity level (hypothesizing a direct relationship between activity and weight loss (Boan 2004)), and surgical technique (hypothesizing greater weight loss maintenance with longer length of the bypass limb in gastric bypass surgery (Choban 2002, Brolin 2002)).

Diabetes Mellitus and Insulin Resistance. Type 2 diabetes mellitus (T2DM), the metabolic syndrome, and insulin resistance (IR) are common metabolic co-morbidities of obesity (Curtis 2005). Assessing the longer-term efficacy of bariatric surgery with respect to T2DM will be based on a clinical history of medication use and on serial measurements of HbA1c. Assessing efficacy for metabolic syndrome and IR will be based on changes in fasting glucose, insulin, lipoprotein profiles, resting blood pressure, waist circumference and clinical history of medications for treatment of hyperglycemia, hypertension, and dyslipidemia.

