It is hypothesized that improvement of T2DM, metabolic syndrome, and IR will be related to maximal weight loss, maximal loss of fat mass, nadir BMI and physical activity level (Sjostrom 1999, Cummings 2004, Sugerma 2003, Greenway 2002, Orchard 2005).

Cardiovascular and Pulmonary Disease. Obesity is a risk factor for cardiovascular diseases (CVD) and sleep apnea (Guisti 2004, de Leiva 1998, Koch 1999, Valencia-Flores 2004, Vendrell 2004, Infanger 2003, Buchwald 2004). To assess the efficacy of bariatric surgery with respect to CVD, changes in the traditional factors listed above for IR as well as high-sensitivity C - reactive protein (hsCRP), a marker of systemic inflammation, will be measured. It is hypothesized that improvement of

CVD factors will be related to maximal weight loss, maximal loss of fat mass, and nadir BMI post surgery (Christ 2004, Reinehr 2004, Blumenthal 2000, Stefanick 1998, Schotte 1990). In addition, change in cardiac function will be measured by the time to complete a 400 meter corridor walk. It is hypothesized that the time to complete the 400 meter corridor walk will be directly related to age, degree of obesity (body mass index [BMI]), sex (longer in females), physical activity level, measures of diabetes mellitus (DM) and insulin resistance (IR), blood pressure (BP), liver function tests, inflammatory markers, and sleep apnea (Newman 2003). Furthermore, the time to complete the corridor walk is hypothesized to predict future events such that increased time or inability to complete the walk is related to subsequent cardiovascular clinical events and mortality (Miyamoto 2000, Zugck 2000). We will also evaluate the incidence of coronary heart disease, defined as sudden death, myocardial infarction or need for coronary revascularization post surgery. It is hypothesized that patients who are male and patients who have unchanging metabolic profiles associated with diabetes or PCOS will be at higher risk (Talbot 2004, Kannel 1979).

The prevalence of sleep apnea and changes from baseline status will be assessed by self-report via the Berlin Sleep Questionnaire and by use of continuous or bilevel positive airway pressure machines (CPAP or BiPAP). It is hypothesized that weight loss and reductions in neck circumference will be associated with improvements in sleep apnea.

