Behavioral Factors. Evidence suggests that pre-existing psychological and behavioral problems influence the outcomes, both short-term and long-term, of bariatric surgery (Herpertz 2004). In particular, it is hypothesized that subjects who have active untreated problems with alcohol or drug abuse, problems with binge eating, or problems with untreated depression will experience higher rates of surgical post-operative medical complications, less weight loss (Hsu 1998, Hsu 1996, Hsu 1997, Green 2004, Averbukh 2003), and less relative improvement in social functioning, quality of life, depression, and overall psychological status (Green 2004), while those who intentionally lose weight pre-operatively (van de Weijert 1999) and those with more family/social support (Ray 2003, Hildebrandt 1998) will achieve greater weight loss. Furthermore, it is hypothesized that bariatric surgery will result in substantial improvements in social functioning (Choban 1999), quality of life (Dymek 2001), depression (Dixon 2003, Dymek 2001), and overall psychological status (Hsu 1998). The magnitude of the improvement in these parameters will positively correlate with the degree of weight loss. Additionally, depression that reoccurs or develops post-operatively will be associated with decreased improvement in quality of life (Moore 2005).

Gender Issues. Potential gender differences in longer-term efficacy of bariatric surgery for weight loss, maintenance of weight loss, prevalence of T2DM, parameters of metabolic syndrome, insulin resistance and magnitude of CVD risk factors will be examined. It is hypothesized that baseline insulin resistance severity will be more important than gender as a predictor of efficacy of bariatric surgery for DM and CVD risk factors. LABS-2 will also examine whether changes in sexual functioning are related to weight loss (Larsen 1990, Camps 1996, Trischitta 2003)

Women's Health. Women constitute the majority of patients who undergo bariatric surgery. Obesity is a risk factor for several health conditions specific to, or more common among, women, such as menstrual abnormalities (Norman 2004), infertility (Norman 2004), and urinary incontinence (Kapoor 2004). It is hypothesized that menstrual abnormalities (Crosignani 2003), fertility (Gerrits 2003), symptoms of polycystic ovarian diseases (Crosignani 2003), and urinary incontinence (Sugerman 2001)

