2.2 Secondary Objectives

1. To assess health care utilization of patients undergoing bariatric surgery for treatment of obesity and related co-morbidities.
2. To obtain and store biospecimens (serum, plasma, urine and tissue) for research related to the aims of LABS-2, and for future research into the pathophysiology of obesity and obesity related complications.

Specific hypotheses to be investigated from these secondary objectives are described below:

Health Care Utilization. Patient outcome following bariatric surgery is variable, and hence, so is subsequent use of health services. It is hypothesized that higher levels of BMI pre-surgery will be associated with higher post-surgery health services utilization; hospital readmission rates will be higher for patients who undergo BPD-DS compared to other surgical procedures; and patients who are more physically active following surgery will utilize fewer health services.

Biospecimens. Approximately, 55.5mL of blood and 4.5 of urine will be obtained from LABS-2 participants at pre-specified intervals (see §3.4). Fasting insulin, high sensitive C-reactive protein, lipid profile (HDL, LDL, total cholesterol, triglycerides), HbA1C, serum creatinine, cystatin C, urine creatinine, and urine albumin will be measured at a central laboratory. Aliquots of plasma and serum will be banked for future investigations into parameters such as changes in metabolic parameters and markers of risk. An additional 24mL of whole blood will be drawn to be used for DNA analysis. Additionally, if a liver biopsy is taken during surgery as part of the clinical institution's standard practice, a small portion will be studied by LABS investigators. Non-LABS investigators may access biospecimens through application via the LABS ancillary studies process or a process to be developed by the NIDDK Biospecimens Repository, where the specimens will be stored indefinitely. A spot urine test will be obtained and sent to a central laboratory for creatinine and albumin determinations. Aliquots of urine will be stored at the NIDDK Repository for use in future substudies on nutrition (e.g. – to measure bone markers).

3 Study Design

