Liver fibrosis severity	Categorical	Hepatic iron accumulation	Continuous	Patient	Ordinal logistic regression
Behavioral Factors:					
Surgical post-discharge medical complications	Categorical	Pre-op untreated alcohol/drug abuse, binge eating, untreated depression	Categorical	Patient	Logistic regression
Δ in body weight	Continuous			Patient/Visit	ANCOVA, linear mixed models, piece-wise linear mixed models, non-linear hierarchical models
Δ in social functioning	Continuous			Patient/Visit	
Δ in quality of life	Continuous	Time since surgery, degree of weight loss	Continuous	Patient/Visit	
Δ in psychological status	Categorical			Patient/Visit	
Δ in body weight	Continuous	Intentional pre-op weight loss	Continuous	Patient/Visit	Linear regression, linear mixed models, piece-wise linear mixed models, non-linear hierarchical models
		Extent of family/social support	Continuous	Patient/Visit	
Δ in quality of life	Continuous	Re-occur/post-op depression	Categorical	Patient/Visit	ANCOVA, linear mixed models
Gender Issues:					
Reduction in diabetes	Categorical	Gender	Categorical	Patient/Visit	Logistic regression, GEE
Δ in CVD risk factors	Categorical	Insulin resistance severity	Continuous	Patient/Visit	
Δ in sexual functioning	Continuous	Weight loss	Continuous	Patient/Visit	Linear regression / mixed models
Urinary incontinence	Categorical				

Table 4.1. (continued). Primary Analytic Methods Used to Evaluate LABS-2 Hypotheses

Outcome Variable	Measurement	Predictor Variable(s)	Measurement	Unit of Analysis	Primary Method(s) Of Analysis
Women’s Health:					
PCOS, menstrual abnormalities, infertility	Categorical	Time: PCOS, menstrual abnormalities, and infertility status before surgery and during follow-up after surgery	Categorical	Patient	McNemar’s chi-square test
Risks of Bariatric Surgery:					
Complications – death, outlet obstruction, wound complications, surgical revision, re-operation	Categorical	Sex, race, pre-op comorbidities Pre-op BMI	Categorical Continuous	Patient	Survival analysis, Cox regression
Stomal ulcer, PE/DVT, dehydration	Categorical	Type of anastomoses used, limb length, pouch size	Categorical Continuous	Patient	Survival analysis, Cox regression
Nutrient Deficiencies:					
Protein malnutrition (albumin)	Categorical	Δ in body weight	Continuous	Patient	Logistic regression, GEE
Anemia	Categorical	Limb length, pouch size	Continuous	Patient	
Fat soluble vitamin deficiency	Categorical	Type of surgical procedure	Categorical	Patient	

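### In the insulin-resistance-versus-gender hypothesis, fasting insulin and glucose can sit in both predictor and CVD outcome, so shared baseline error can tilt the comparison towards insulin resistance

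*Protocol*

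**What the plan says.** Four places in the protocol have to be read together.

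- Section 2.1, Diabetes Mellitus and Insulin Resistance, gives one list for metabolic syndrome and insulin resistance (IR): "Assessing efficacy for metabolic syndrome and IR will be based on changes in fasting glucose, insulin, lipoprotein profiles, resting blood pressure, waist circumference", together with medication history.
- Section 2.1, Cardiovascular and Pulmonary Disease, takes its efficacy measures from that list and adds hsCRP: "changes in the traditional factors listed above for IR as well as high-sensitivity C". No other list for IR comes before it.
- Section 2.1, Gender Issues, states the hypothesis: "baseline insulin resistance severity will be more important than gender as a predictor of efficacy of bariatric surgery for DM and CVD risk factors".
- Table 4.1, Gender Issues, sets this up as "Δ in CVD risk factors" (categorical) on "Insulin resistance severity" (continuous), analysed by "Logistic regression, GEE".

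Section 2.2 lists fasting insulin among the central laboratory assays ("Fasting insulin, high sensitive C-reactive protein, lipid profile (HDL, LDL, total cholesterol, triglycerides), HbA1C"). The protocol does not define the severity index. It does not remove insulin or glucose from the CVD outcome for this hypothesis. The confounder rule in section 4.1.3.1, which adjusts for covariates that move the estimate by 10% or more, does not deal with error common to predictor and outcome.

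**The concern.** A change score contains the baseline reading with a minus sign. If the predictor is built from the same reading, a patient whose baseline insulin is high by chance looks more insulin resistant and then appears to improve more, even if surgery acts equally on everyone. This is regression to the mean.

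The hypothesis compares two predictors. Gender has no measurement in common with the outcome and can gain nothing from this. For the overlapping components the comparison is therefore unequal, in the direction that the hypothesis favours. A finding that IR severity outranks gender could not be separated from the artefact.

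**Working it through.** **Inputs from the protocol.** Target 2,400 with up to 25% loss (section 4.4.1), so 2,400 × 0.75 = 1,800 analysed. About 84% women (section 3.2.6), so 16% men. Two-sided alpha 0.05 (section 4.2). Logistic model (Table 4.1). The protocol states no figure for this analysis, so there is none to reproduce.

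**Assumptions (not in the protocol).** Reliability r of a reading, 0.80 to 0.95. SD of true change s, 0.5 to 1.0 in units of the true baseline SD. IR index = log insulin + 0.4 × log glucose. Correlations between factors 0.3 to 0.5. Outcome = improvement above the median.

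**Step 1, closed form.** Let baseline be T + e0 and follow-up T + c + e1, with Var(T) = 1, c independent of T, and error variance v = (1 − r)/r. The covariance of baseline with change is −v, so

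corr = −v / √[(1 + v)(2v + s²)].

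With s = 0 this reduces to −√[(1 − r)/2]: −0.32, −0.22 and −0.16 at r = 0.80, 0.90 and 0.95. With spread in true change:

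- r = 0.80 (v = 0.25): −0.25/√(1.25 × 0.75) = −0.26 at s = 0.5; −0.25/√(1.25 × 1.5) = −0.18 at s = 1.0.
- r = 0.95 (v = 0.0526): −0.0526/√(1.0526 × 0.355) = −0.09 at s = 0.5; −0.0526/√(1.0526 × 1.105) = −0.05 at s = 1.0.

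True change is unrelated to true baseline throughout, so the whole correlation is artefact.

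**Step 2, simulated null.** IR and sex were in one logistic model, with 2,000 patients and 300 runs per cell. The table gives the OR per SD of IR for improved insulin, with the rejection rate.

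| Reliability | s = 0.5 | s = 1.0 |
|---|---|---|
| 0.80 | 1.42 (100%) | 1.28 (100%) |
| 0.90 | 1.22 (99%) | 1.13 (79%) |
| 0.95 | 1.12 (71%) | 1.06 (24%) |

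Over the same range, rejection for improved glucose was 9% to 87%. A lipid-type factor sharing no measurement gave OR 1.00 with 3-6% rejection. Sex gave 4-6%. The simulation error at 5% is √(0.05 × 0.95/300) = 1.3 percentage points, so these last two are nominal.

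**Step 3, at 1,800 patients.** False rejection for IR was 24-100% for insulin, 13-83% for glucose and 12-98% for a composite of eight factors (insulin, glucose, HDL, LDL, triglycerides, blood pressure, waist and hsCRP), against about 5% for a non-overlapping factor and 3-8% for sex. A separate eight-factor run gave 10-97%, with OR 1.03 to 1.20.

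**Step 4, the comparison with gender.** With neither predictor having a true effect, IR had the larger test statistic in 55-100% of runs for an overlapping outcome and about 50% otherwise.

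**Step 5, coding.** Table 4.1 does not say how change is made categorical. If it means falling below a cut-point among patients above it at baseline, the same null was rejected in every run, with an OR well below 1, because distance to the cut-point decides the result. The sign depends on the coding, but IR still outranks gender.

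**The case against.** The strongest reply is that the protocol does not fix the overlapping analysis. Much of it stands.

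- **The index is undefined.** One might infer that IR severity is built from fasting insulin and glucose. The protocol does not say so, and the choice may properly sit in an analysis plan. The point is therefore conditional. Other indices would move the overlap: if IR is read as the whole list in section 2.1, it widens.
- **Gender Issues treats insulin resistance and CVD risk factors as separate items**, and Table 4.1 carries change in insulin resistance as its own outcome elsewhere. That is a fair reading. However, the only statement of what the CVD factors are is the cross-reference in the cardiovascular paragraph, and it leads to a list naming insulin and glucose. The text allows both readings.
- **No composite is specified.** If each factor is analysed alone, lipids, blood pressure and hsCRP are already free of the artefact under an insulin/glucose index. Only the insulin and glucose results, or a summary including them, are affected.
- **The size depends on assumptions.** A reader might take false rejection to be near 100%, with an OR of about 1.5 per SD. That is the worst case, in which one measure of reliability 0.80 serves as both predictor and outcome. At reliability 0.95 and s = 1.0 it is 24% for insulin.
- **Section 4.1 leaves the final method open.** That permits a correction but does not provide one.

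A reader might also infer that the artefact explains the whole hypothesis. It does not: diabetes efficacy rests on HbA1c and medication history, which share no insulin or glucose assay with such an index.

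**Conclusion.** The point holds in a limited, conditional form. Read literally, section 2.1 places changes in fasting insulin and glucose among the CVD risk factors that Table 4.1 predicts from IR severity. If severity is a fasting insulin or insulin/glucose index, shared baseline error alone can create an association for those components and any summary containing them, and so favour IR over gender.

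The size runs from modest to overwhelming across the assumed reliability and spread of true change, neither of which the protocol gives. The documents do not support the stronger statement that measurement error produces the association across CVD risk factors generally. A real relation may also exist; for the overlapping components the planned analysis cannot tell the two apart.

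**What to change.** In section 2.1 (Gender Issues) and in the matching row of Table 4.1, state that for this hypothesis:

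- the CVD risk-factor outcome excludes fasting insulin, fasting glucose and any other component of the chosen IR index;
- the remaining factors (lipids, blood pressure, waist circumference, related medication and hsCRP) are kept and analysed separately;
- change in insulin and glucose by baseline IR is reported descriptively only.

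Name the IR index in the same place, because the exclusion depends on it. In the simulation, a factor sharing no measurement with the index had nominal error.

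The cost is a short edit and no new data. Two factors are lost from this one hypothesis test, or more if the chosen index has other components. Other uses of insulin and glucose in the protocol are unaffected.

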Renal Disease. Obesity causes and complicates diabetes and hypertension, the two most common causes of kidney failure (Wiggins 2005). Furthermore, obesity in its own right can cause renal disease and may accelerate injury in glomerulonephritides (De Jong 2002). The mechanisms for the adverse effects of obesity on the kidney include its hypertensive and diabetogenic effects. Additionally, adipogenic hormones may have direct injurious actions in the kidney (Coresh 2004). Thus, weight loss is likely to improve indices of renal function. However, bariatric surgery itself has been associated with progressive renal disease through a variety of mechanisms (Khurana 2004). Renal function will be measured by serum creatinine and cystatin and urinary albumin and creatinine (spot urine).

It is hypothesized that albuminuria, the most sensitive index of chronic kidney disease, will diminish after successful bariatric surgery and that the renal function as reflected by serum creatinine will remain stable after successful bariatric surgery (Holzwarth 2002).

Liver Function and Size. The apparent increased prevalence of various forms of non-alcoholic fatty liver disease (NAFLD) in the obese population (Haynes 2004), and the growing identification of NAFLD when sought by liver biopsy among patients undergoing bariatric surgical procedures (Abrams, 2004) have both been the subject of recent publications. The limited data available thus far indicate that it would be important to determine the presence of NAFLD and define the prevalence of advanced forms, such as non-alcoholic steatohepatitis (NASH) and cryptogenic cirrhosis, by systematic intra-operative liver biopsy in a well defined bariatric surgical population. When a liver biopsy is taken during surgery as part of the clinical institution's standard practice, a portion will be studied by LABS investigators. The thickness of the left lobe of the liver will be assessed using a standardized measuring technique.

It is hypothesized that the prevalence and severity of the spectrum of non-alcoholic fatty liver disease are underestimated by traditional laboratory parameters, clinical assessment, and intra-operative visual inspection of the liver (Gholam 2002, Spaulding 2003). Additionally, it is hypothesized that severity of

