Variable	Measurement	Variable(s)	Measurement		
Weight Loss and Body Composition:					
Max. weight loss	Continuous	Gender, diabetes, surgical technique	Categorical	Patient	Analysis of covariance (ANCOVA)
Max. Δ in fat mass	Continuous				
Max. Δ in fat free mass	Continuous	Physical activity level (pre-op and post-op)	Continuous	Patient	Linear regression
Max. Δ in waist circumference	Continuous				
Max. Δ in neck circumference	Continuous				
Patterns of weight loss	Continuous	SAME AS ABOVE	SAME AS ABOVE	Visit	Linear mixed models, piece-wise linear mixed models, non-linear hierarchical models
Pattern of weight regain	Continuous				
Diabetes Mellitus & Insulin Resistance:					
Reduction in diabetes	Categorical	Maximal weight loss, maximal loss of fat mass, nadir BMI	Continuous	Patient/Visit	Logistic regression, Discrete-time proportional hazards (pooled logistic regression)
Reduction in met. syndrome	Categorical				
Δ in insulin resistance	Continuous				
CVD and Pulmonary Disease:					
Corridor walk time	Continuous	Age, BMI, insulin resistance, blood pressure, liver function, inflammatory markers	Continuous	Patient	Spearman correlation, linear regression
Corridor walk time	Continuous	Gender, diabetes, sleep apnea	Categorical	Patient	ANCOVA
Incident CVD, mortality	Categorical				
Renal Disease:					
Δ in albuminuria	Continuous	Pre/post bariatric surgery	Continuous	Patient	Paired t-tests or analogous non-parametric methods
Δ in GFR	Continuous	Pre/post bariatric surgery	Continuous	Patient	

Table 4.1. (continued). Primary Analytic Methods Used to Evaluate LABS-2 Hypotheses

Outcome Variable	Measurement	Predictor Variable(s)	Measurement	Unit of Analysis	Primary Method(s) Of Analysis
Liver Function:					
Prevalence/severity of non-alcoholic fatty liver disease (NAFLD) (based on histology)	Categorical	Traditional assessment of NAFLD (labs, clinical assessment, visual inspection)	Categorical	Patient	Kappa statistic, predictive value negative
		Race/ethnicity, traditional demographic, clinical, and laboratory assessments	Categorical and continuous	Patient	Binomial and ordinal logistic regression
Short-term post-operative morbidity and mortality	Categorical	Severity of liver disease (biopsy)	Categorical	Patient	Poisson regression
Δ in liver disease (clinical and biochemical)	Continuous	Steatohepatitis (detected on biopsy), weight loss	Categorical	Patient/visit	Linear regression / linear mixed models

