4.1.3.2 Assessment of Effect Modification. Many analyses anticipated will involve subgroup comparisons of the efficacy of bariatric surgery – in other words, do all patients achieve the same degree of benefit from weight loss surgery? To assess whether the effect of bariatric surgery is modified by specific patient characteristics, two primary approaches will be employed. These include stratified analyses to compare estimates of effect across levels of patient characteristics, and more formal tests of interaction. Formal tests of interaction are not selected as the primary analytic approach for the simple reason that they are heavily influenced by the sample size of the subgroups involved, and hence, often underpowered to detect meaningful interactions.

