4.2. Sample Size Estimates. As listed in Section 2.1, LABS-2 will evaluate the efficacy of bariatric surgery using a wide range of patient outcomes with various scales of measurement and across many scientific disciplines. Moreover, additional hypotheses regarding the efficacy of bariatric surgery will be developed and evaluated during the course of the study. For these reasons, sample size calculations have been provided for both binary and continuous outcome measures, assuming either single or repeated measurements, and assuming varying proportions of patients within subgroups to be compared. For simplicity, patient and surgical characteristics to be compared are based on two-group comparisons, recognizing that some characteristics may be evaluated using more than two groups and with alternative statistical methods, such as linear tests of trend. Finally, to be conservative, all calculations are based on desired power of at least 90% and two-sided alpha of 0.05.

4.2.1. Comparisons of Proportions Based on Single Outcome Measurement. Table 4.2.2 presents odds ratios detectable at 90% power for comparing binomial proportions of outcome occurrence given various sample sizes, event rates in the reference (control) group, and percentage of all subjects as controls. As seen, with an effective sample size ranging from 1200 to 3200 patients, detectable odds ratios range from 1.32 to 3.10. With the goal of having sufficient statistical power to detect odds ratios of 2.0 or higher, an effective sample size of 2000 patients is sufficient for all conditions with the exception of when a low event rate of 5% is observed in the reference subgroup coupled with a highly imbalanced design in which 90% of all subjects reside within the reference subgroup. Of note, these binomial comparisons of event rates and detectable odds ratios are conservative with respect to the frequent anticipated use of alternative survival analysis methods, when appropriate.

Table 4.2.2. Odds Ratios Detectable at 90% Power Given Various Sample Sizes, Event Rates in Control Subjects (Reference Group) and Proportions of Subject in Reference Group*

Sample Size % of reference group →	5% event rate in reference group			10% event rate in reference group			20% event rate in reference group		
	50%	75%	90%	50%	75%	90%	50%	75%	90%
1200	2.13	2.33	3.10	1.78	1.91	2.44	1.57	1.67	2.05
1400	2.03	2.21	2.90	1.71	1.83	2.30	1.52	1.61	1.95
1600	1.95	2.11	2.74	1.65	1.77	2.19	1.48	1.56	1.88

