4.3. Comparisons of Continuous Outcome Variables Based on Single Outcome

Measurement. Table 4.4 presents effect sizes (difference in mean scores between the 2 groups being compared / common standard deviation) detectable at 90% power given various sample sizes and proportion of all subjects in the control (reference) group. As seen, with an effective sample size ranging from 1200 to 3200 patients, detectable effect sizes range from 0.11 to 0.31. In general, effect sizes less than 0.2 are considered “small” and those from 0.2 to <0.5 are considered “medium” (Cohen 1988). Thus, an effective sample size of 1800 subjects will be sufficiently powered to detect “small” effect sizes under all conditions with the exception of a highly imbalanced design in which 90% of all subjects reside within the reference subgroup.

[figure not shown]
Table 4.4. Effect Sizes for Continuous Outcome Measures Detectable at 90% Power Given Various Sample Sizes and Proportions of Subjects in the Reference Group*

Sample Size	% of All Subjects in Reference Group				
	50%	60%	70%	80%	90%
1200	0.19	0.19	0.20	0.23	0.31
1400	0.17	0.18	0.19	0.22	0.29
1600	0.16	0.17	0.18	0.20	0.27
1800	0.15	0.16	0.17	0.19	0.25
2000	0.15	0.15	0.16	0.18	0.24
2200	0.14	0.14	0.15	0.17	0.23
2400	0.13	0.14	0.14	0.17	0.22
2600	0.13	0.13	0.14	0.16	0.21
2800	0.12	0.13	0.13	0.15	0.20
3000	0.12	0.12	0.13	0.15	0.20
3200	0.11	0.12	0.13	0.14	0.19

*Based on Student’s *t* test and assuming 2-sided alpha of 0.05.

4.4.1. Target Sample Size. Based on the above sample size calculations and the desire to be able to detect odds ratios of at least 2.0 for categorical outcomes and “small” effect sizes for continuous outcomes, a target sample size of 2,400 patients is proposed. This exceeds the estimates of 2,000 patients for discrete outcomes under most circumstances (table 4.2) and 1800 patients for continuous outcomes (table 4.4) so as to conservatively allow for loss to follow-up ranging from approximately 16% to 25%.

5 Study Organization

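### The hypothesis that renal function stays stable is assigned a paired difference test, whose null hypothesis is the claim itself, so the stated method cannot support it

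*Protocol*

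**What the plan says.** The renal paragraph of Protocol section 2.1 holds two hypotheses of different kinds. Albuminuria is expected to fall. For filtration the expectation is no change: "the renal function as reflected by serum creatinine will remain stable after successful bariatric surgery". The same paragraph gives reasons to look in both directions, since weight loss may improve renal indices and surgery has been linked to progressive renal disease.

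Section 4.1.2 presents Table 4.1 as defining the primary methods. Its renal block lists change in albuminuria and change in GFR, each as a patient-level pre/post comparison, with one entry for method: "Paired t-tests or analogous non-parametric methods". In the extracted text that entry stands on the albuminuria row and the GFR cell is blank. A merged cell is the natural reading. Serum creatinine, the measure named in the hypothesis, has no row.

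Section 4.2 states that "all calculations are based on desired power of at least 90% and two-sided alpha of 0.05". In section 4.4.1 "a target sample size of 2,400 patients is proposed", with an allowance for "loss to follow-up ranging from approximately 16% to 25" per cent. The protocol does not say what counts as stable.

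**The concern.** A paired t-test, or a signed-rank test in its place, asks whether the data contradict a mean or median change of zero. That suits albuminuria, where the study hopes to reject. For the stability hypothesis the roles are reversed: the study hopes the null is true, and the test cannot deliver that conclusion. A large sample rejects it for changes of no importance, and a small sample fails to reject it whatever the truth. A statement about renal function, which belongs to the longer-term safety aim in section 2.1, could then follow the number of patients analysed more than the size of the renal change.

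**Working it through.** **The plan's own figure.** The protocol gives no power calculation for a paired comparison. The nearest figure is Table 4.4: two groups, N = 2,400, half in the reference group, 90% power, detectable effect 0.13. The formula is d = (z₀.₉₇₅ + z₀.₉₀) × √(1/n₁ + 1/n₂) = (1.960 + 1.2816) × √(1/1200 + 1/1200) = 3.2416 × 0.0408 = 0.132, which agrees. The same formula reproduces every cell of Table 4.4 within rounding.

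**Evaluable patients.** Section 4.4.1 sets 2,400 against requirements of 2,000 and 1,800: 1 − 2000/2400 = 16.7% and 1 − 1800/2400 = 25%. The lower number, 1,800, is used below. The hypothesis is limited to successful surgery, which the renal paragraph does not define, so the number analysed could be smaller.

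**Paired test, two-sided 0.05, in units of the SD of individual change.** The smallest significant observed mean change is 1.96/√n. The change detectable at 90% power is (1.96 + 1.2816)/√n.

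| n | significant at | 90% power at | power if true change is 0.1 SD |
|---|---|---|---|
| 2,400 | 0.040 | 0.066 | 99.8% |
| 1,800 | 0.046 | 0.076 | 98.9% |

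For comparison, section 4.3 says "In general, effect sizes less than 0.2 are considered" small.

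**Scale check.** Section 4.3 standardises by the SD between patients, and the paired test by the SD of change. With equal SDs before and after and correlation r, SD of change = SD × √(2(1 − r)). At r = 0.5 the two are equal, and at higher r the detectable change is smaller still on the between-patient scale. Even at r = 0 the figures at n = 1,800 become 0.046 × 1.414 = 0.065 and 0.076 × 1.414 = 0.107, both below 0.2.

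**In creatinine units (assumption: SD of change 0.10 to 0.20 mg/dL, not in the documents).** At n = 1,800 the test is significant from 0.0462 × 0.10 = 0.0046 to 0.0462 × 0.20 = 0.0092 mg/dL.

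**Fewer patients (illustrative n = 60, not tied to any renal analysis in the plan).** A true change of 0.2 SD is non-significant 67% of the time, and 0.3 SD 37% of the time.

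**Feasibility of an equivalence rule (margins are assumptions).** Two one-sided tests at 0.05 each, true change 0, 90% power: n = ((1.645 + 1.645)/margin)².
- Margin 0.2 SD: (3.290/0.2)² gives 271.
- Margin 0.1 SD: (3.290/0.1)² gives 1,083.

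Both are below 1,800. With 1,800 patients and a 0.2 SD margin, power is at least 99.5% for a true change of 0 to 0.1 SD. With 60 patients the 90% interval has half-width 1.645/√60 = 0.212 SD. This exceeds 0.2, so that margin could not be met and stability could not be declared by default.

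**The case against.** The strongest reply is that the protocol misuses nothing. A reader might infer that a non-significant result will be reported as stability, or a significant one as its refutation. The protocol says neither. A paired analysis also yields an estimate and an interval, and sections 4.1.3.1 and 4.1.3.2 show that the authors are wary of criteria driven by sample size. That stands. The finding is that the named method does not match the hypothesis, not that a wrong conclusion is planned.

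A reader might also infer that a renal subgroup will be declared stable for want of power. Section 4.1.3.2 does plan "stratified analyses to compare estimates of effect across levels of patient characteristics", but that is general. No renal subgroup is named, so the small-sample arithmetic is only an illustration.

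Nor should the GFR difference test be dropped. Section 2.1 raises both improvement and decline, and a two-sided paired comparison addresses that question properly.

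An equivalence margin may stand in an analysis plan that is not shown, so its absence alone is not the point. Section 4.1 also lets the final method depend on what suits the data. That softens the commitment to the t-test but supplies no criterion for stability, and Table 4.1 still names a primary method that cannot support the stated hypothesis.

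**Conclusion.** The point holds, at moderate severity. Section 2.1 states a no-change hypothesis and Table 4.1 gives it a test of no change. At the protocol's own evaluable number the test is significant at 0.046 SD, under a quarter of the protocol's 0.2 limit for a small effect (0.046/0.2 = 0.23). In smaller analyses a non-significant result says little. There is a secondary mismatch, since the hypothesis names serum creatinine and the table names GFR. The flaw is the same for either measure.

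The conclusion rests on reading the method cell as covering the GFR row, on applying the alpha of section 4.2 to this test, and on 1,800 evaluable patients. It does not depend on the creatinine SDs or the margins, which are assumptions for illustration. It affects one inference among many in an observational cohort. The target of 2,400 does not rest on it, so calling it critical to the study would overstate it.

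**What to change.** In the renal block of Table 4.1:

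- Keep the paired estimate of pre/post change with its confidence interval, so that improvement or decline can still be detected.
- Name the measure for the stability hypothesis: either serum creatinine, with its own row, or GFR, with section 2.1 reworded to match.
- Add that stability is concluded only if the 90% confidence interval for mean change lies wholly within an equivalence margin, which the investigators choose and justify before the renal change data are analysed.
- State that a non-significant difference is not read as stability.

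The albuminuria row needs no change.

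The cost is a sentence or two in the table and agreement on a margin, with no new data and no change in sample size. Agreeing the margin in advance is the real effort. The document is at Version 7 and carries a 2013 amendment, so some renal change data may already have been analysed. If so, the margin should be reported as set afterwards.
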